16.2 CLINICAL TECHNICAL PROCEDURES (CTPS)

Applicable	Codes	Title
		Pre-Ocular and Pre-Lens Wettability
X		Limbal and Conjunctival (BULBAR) Redness
X		Expanded Sodium Fluorescein Corneal Staining
		Determination of Near Addition
		Near LogMAR Visual Acuity Measurement Procedure
		Contact Lens Centration Measurements with a Slit Lamp Reticle
X		Lens Fitting Characteristics
X		Subjective Report Ocular Symptoms / Problems
X		Trapped Back Surface Debris and Mucin Plug Grading Procedure
X		Front and Back Surface Lens Deposit Grading Procedure
		Cornea Striae and Corneal Folds Grading Procedure
		Corneal Microcyst and Vacuole Grading Procedure
		Evaluation of Corneal Vascularization
X		Determination of Distance Spherocylindrical Refractions
		Visual Symptom Frequency Questionnaire
X		Biomicroscopy Scale
		Video Recording for Soft Contact Lens Fitting Measurements
		Tarsal Roughness and Tarsal Redness
X		Conjunctival Staining
		Keratometry Procedure
X		Distance and Near Visual Acuity Evaluation
X		Toric Fit Evaluation
		Upper Lid Margin Staining
X		Distance LogMAR Visual Acuity Measurement Procedure
		Measurement of COAS Wavefront Aberrations
X		White Light Lens Surface Wettability

16.3 PATIENT INSTRUCTION GUIDE (APPROVED PRODUCT)

A Patient Instruction Guide will be provided separately.

16.4 PACKAGE INSERT

A Package Insert will be provided separately.

17.1 LIST OF ABBREVIATIONS

AE	Adverse Event/Adverse Experience
CFR	Code of Federal Regulations
CIB	Clinical Investigator's Brochure
CRF	Case Report Form
CRO	Contract Research Organization
FDA	Food and Drug Administration
GCP	Good Clinical Practice
HIPAA	Health Insurance Portability and Accountability Act
IB	Investigator's Brochure
ICF	Informed Consent Form
ICH	International Conference on Harmonization
IDE	Investigational Device Exemption
IEC	Independent Ethics Committee
IRB	Institutional Review Board
MedDRA ©	Medical Dictionary for Regulatory Activities
MOP	Manual of Procedures
NIH	National Institutes of Health
OHRP	Office for Human Research Protections
OHSR	Office for Human Subjects Research
PHI	Protected Health Information
PI	Principal Investigator
QA	Quality Assurance
QC	Quality Control
SAE	Serious Adverse Event/Serious Adverse Experience
SOP	Standard Operating Procedure
UADE	Unanticipated Adverse Device Effect
USADE	Unanticipated Serious Adverse Device Effect

APPENDIX A: [REDACTED] Limbal & Conjunctival (Bulbar) Redness

Limbal and Bulbar Conjunctival Redness

REDNESS

OD

N	T	I	S

OS

N	T	I	S

LEVEL OF REDNESS: Refer to the Efron Grading Scale

0: Normal

1: Trace

2: Mild

3: Moderate

4: Severe

APPENDIX B: [REDACTED] Expanded Sodium Fluorescein Corneal Staining

APPENDIX C: [REDACTED] Lens Fitting Characteristics

APPENDIX D: [REDACTED] Subject Reported Ocular Symptoms/Problems

APPENDIX E: [REDACTED] Trapped Back Surface Debris and Mucin Plug Grading Procedure

APPENDIX F: [REDACTED] Front and Back Surface Lens Deposit Grading Procedure

APPENDIX G: [REDACTED] Determination of Distance Spherocylindrical Refractions

APPENDIX H: [REDACTED] Biomicroscopy Scale

APPENDIX I: [REDACTED] Conjunctival Staining

APPENDIX J: [REDACTED] Distance and Near Visual Acuity Evaluation

APPENDIX K: [REDACTED] Toric Fit Evaluation

APPENDIX L: [REDACTED] Distance LogMAR Visual Acuity Measurement Procedure

APPENDIX M: [REDACTED] White Light Lens Surface Wettability

APPENDIX N: [REDACTED] Visual Acuity Chart Luminance and Room Illumination Testing

1. INTRODUCTION

1.1. Background

This document describes the data analysis specifications for the protocol CR5871 titled “Evaluation of Astigmatic Contact Lenses”. The test lens is the Johnson & Johnson Vision (JJV) investigational contact lens Atlas A and the control lens is the Alcon Air Optix for Astigmatism® (AOA) which is currently marketed as a monthly replacement.

This Statistical Analysis Plan (SAP) will serve as the final guidance for all the statistical analyses for this study and will supersede the Section 9 in the protocol if there are any discrepancies.

1.2. Study Objectives

The objectives of the study are to demonstrate that the senofilcon C toric in its final lens design meets the design validation requirements related to corneal staining, lens fitting characteristics, visual acuity and rotational performance of senofilcon C toric contact lenses as well as subjective comfort and handling when worn for 30 (-2/±6) days on daily wear modality.

1.3. Study Design

This is a randomized, double-masked, multi-center, bilateral, 5-visit dispensing parallel group design study. Subjects will be randomly assigned to wear one of two study lenses bilaterally for approximately 30 days in a daily wear, monthly replacement modality. Approximately 270 eligible subjects will be enrolled to attain a minimum of 230 subjects to complete the study (115 subjects per arm).

This study consists 5 office visits including an initial visit and 4 subsequent follow-up visits as described in Table 1.

Table 1: Study Time Event Description

Visit Number	Event	Description	Approximate Duration (Hour)
1	Enrollment/ Baseline/ Dispensing	Execute informed consent process, determine eligibility criteria, collect demographics and baseline data, trial fitting/dispensing, and visual performance	2.5
2	1-week Follow-up (6-9 days from Visit 1)	Follow-up visit to assess the study lens performance: subjective responses, visual acuity (VA), fitting characteristics, surface characteristics, and physiology	1.0
3	2-week Follow-up (6-9 days from Visit 2)	Follow-up visit to assess the study lens performance: subjective responses, VA, fitting characteristics, surface characteristics, and physiology	1.5
4	3-week Follow-up (6-9 days from Visit 3)	Follow-up visit to assess the study lens performance: subjective responses, VA, fitting characteristics, surface characteristics, and physiology	1.0
5	4-week Follow-up (6-9 days from Visit 4)	Follow-up visit to assess the study lens performance: subjective responses, VA, fitting characteristics, surface characteristics, and physiology	1.5

Subject will be advised to wear the study lenses for 8 hours each day and to the follow-up visit, after a minimum 8 hours of wear that day. Unscheduled visit(s) may occur during the course of the study if a

subject experiences any investigational device-related difficulties and/or problems requiring an unscheduled visit to the clinic.

1.4. Statistical Hypotheses for Study Objectives

1.4.1. Primary Hypotheses

The co-primary endpoints for this study are:

- Monocular distance visual acuity 20/40 or better,
- Lens fitting acceptability,
- Stability with blink,
- Absolute rotation, and
- Contact lens related corneal staining.

Monocular Visual Acuity (VA) 20/40 or better

The proportion of dichotomized monocular VA 20/40 or better in the Atlas A group will be compared to a historical control proportion (p_0) of 80%. The alternative hypothesis (denoted as H_a) is at least 80% of eyes in the Atlas A group will have monocular visual acuity 20/40 or better throughout all planned visits (Visits 1 through 5) whereas the null hypothesis (denoted as H_0) is less than 80% of eyes in the Atlas A group will have monocular visual acuity 20/40 or better. The following hypothesis testing for proportion will be assessed:

$$H_0: p < p_0 \text{ vs. } H_a: p \geq p_0,$$

where p represents the population proportion and p_0 represents a historical control proportion of 80%.

Lens Fitting Acceptability

The proportion of acceptable lens fit at fitting (Visit 1) in the Atlas A group will be compared to a historical control proportion (p_0) of 80%. The alternative hypothesis is at least 80% of eyes in the Atlas A group will have acceptable lens fit at fitting whereas the null hypothesis is less than 80% of eyes in the Atlas A group will have acceptable lens fit. The following hypothesis testing for proportion will be assessed:

$$H_0: p < p_0 \text{ vs. } H_a: p \geq p_0,$$

where p represents the population proportion and p_0 represents a historical control proportion of 80%.

Stability with Blink

The proportion of dichotomized adequate lens stability with blink (adequate stability is defined as lens stability with blink \leq 5-degree) at fitting (Visit 1) in the Atlas A group will be compared to a historical control proportion (p_0) of 80%. The alternative hypothesis is at least 80% of eyes in the Atlas A group will have adequate lens stability with blink at fitting whereas the null hypothesis is less than 80% of eyes in the Atlas A group will have adequate lens stability with blink. The following hypothesis testing for proportion will be assessed:

$$H_0: p < p_0 \text{ vs. } H_a: p \geq p_0,$$

where p represents the population proportion and p_0 represents a historical control proportion of 80%.

Absolute Rotation

The proportion of dichotomized acceptable absolute rotation (acceptable absolute rotation is defined as absolute rotation \leq 10-degree) at 15-minute post insertion (Visit 1) in the Atlas A group will be compared to a historical control proportion (p_0) of 80%. The alternative hypothesis is at least 80% of eyes in the Atlas A group will have acceptable absolute rotation at 15-minute post insertion whereas the null

hypothesis is less than 80% of eyes in the Atlas A group will have acceptable absolute rotation. The following hypothesis testing for proportion will be assessed:

$$H_0: p < p_0 \text{ vs. } H_a: p \geq p_0,$$

where p represents the population proportion and p_0 represents a historical control proportion of 80%.

Contact Lens Related Corneal Staining (CS)

The proportion of dichotomized unacceptable contact lens related CS (unacceptable CS is defined as CS grade 3 or higher) in the Atlas A group will be compared to the proportion of that in the AOA group throughout all planned and unplanned visits. The alternative hypothesis is the odds of unacceptable CS incidence rate in the Atlas A group ($OR_{Atlas A}$) is not statistically different from the odds of that in the AOA group (OR_{AOA}) throughout the wear period. The following hypothesis testing for odds ratio will be assessed:

$$H_0: OR = 1 \text{ vs. } H_a: OR \neq 1,$$

where OR represents the ratio of $OR_{Atlas A}$ over OR_{AOA} ($OR_{Atlas A}/OR_{AOA}$) and Ψ_0 represents a margin of 1 that reflects distribution similarity between the Atlas A and AOA groups.

1.4.2. Secondary Hypotheses

The secondary endpoints for this study are:

- Monocular distance visual acuity 20/20 or better,
- CLUE Comfort Score, and
- CLUE Handling Score.

Monocular Visual Acuity (VA) 20/20 or better

The proportion of dichotomized monocular VA 20/20 or better in the Atlas A group will be compared to the proportion of that in the AOA group at fitting (Visit 1). The alternative hypothesis is the odds of the proportion of eyes with monocular VA 20/20 or better in the Atlas A group ($OR_{Atlas A}$) is not inferior to the odds of that in the AOA group at fitting. The following hypothesis testing for odds ratio will be assessed:

$$H_0: OR \leq \Psi_0 \text{ vs. } H_a: OR > \Psi_0,$$

where OR represents the ratio of $OR_{Atlas A}$ over OR_{AOA} ($OR_{Atlas A}/OR_{AOA}$) and Ψ_0 represents a non-inferiority margin (0.5) that reflects 10% difference in distribution between the Atlas A and AOA groups using the reference rate of 89%.

CLUE Score

The overall means of CLUE comfort and handling scores in the Atlas A group will be separately compared to the overall means of that in the AOA group considering all planned visits (fitting and 4 subsequent follow-up visits). The alternative hypothesis is the overall mean CLUE score in the Atlas A group is not inferior to that in the AOA group. The minimum clinically relevant difference (Δ , delta) between the Atlas A and AOA groups is set to -5 which translates into 10% shift in the CLUE score distribution. The following hypothesis testing for overall mean difference will be assessed:

$$H_0: \mu_{Atlas A} - \mu_{AOA} \leq \Delta \text{ vs. } H_a: \mu_{Atlas A} - \mu_{AOA} > \Delta,$$

where $\mu_{Atlas A}$ and μ_{AOA} represent overall means in the Atlas A and AOA groups, respectively.

1.5. Sample Size Justification

Sample size was calculated to attain the optimal number of subjects to demonstrate the statistical acceptance of the primary and secondary hypotheses using the historical data from CR5699 and CR5799. The incidence rates (%) of the primary endpoints from the historical data are presented in Table 2 below.

Table 2: Incidence Rate (%) from the Historical Data

Endpoints	Event	Atlas A Rate (%)	AOA Rate (%)
Monocular Visual Acuity 20/40 or better	Overall	100	100
Monocular Visual Acuity 20/20 or better	Overall	93.2	92.9
Corneal Staining < Grade 3*	Overall	100	100
Acceptable Lens Fit	Fitting	100	100
Absolute Rotation within 10-degree	15-min	97	96
Stability with Blink within 5-degree	Fitting	100	100

*Corneal staining will be assessed to demonstrate no difference between the Atlas A and AOA lenses whereas the other primary endpoints will be assessed to demonstrate satisfying a minimum threshold (80%) of the Atlas A.

Primary Endpoints with a 80% Threshold:

The common reference rate of 95% was selected for the sample size calculation as all applicable primary endpoints are binary in nature. Assuming a correlation of 0.8 between eyes, 2000 trials (replicating 2000 trials) were simulated to attain a sample size with a minimum statistical power of 90%.

Primary Endpoints with No Difference:

The incidence reference rate of 0.005% was selected for the sample size calculation for no difference between two study lenses on corneal staining grade 3 or higher using the formula given by Diggle et al. (2002¹) for cluster binary data. The incidence rate of 0.005% was set considering the 5 previous Atlas studies (both sphere and astigmatism) including CR5417, CR5582, CR5726, CR5699 and CR5799. There were no incidences of corneal staining grade 3 or higher among all 5 studies, hence it was deemed that 0.005% is a reasonable incidence rate. The number of observations per subject (cluster) was set to 2 (2 eyes per subject) and a correlation between eyes within a subject was set to 0.3 to attain a sample size with a minimum statistical power of 80%.

Secondary Endpoint:

Sample size calculation for the overall CLUE comfort was also performed considering the effect size of 5 (Atlas A -AOA) to achieve a minimum statistical power of 90%. The 2000 trials were simulated for the repeated measurements from the multivariate normal distribution at a 5% significance level using the following covariance attained from the historical data:

Test:

$u_{11} = 365.99$
 $u_{21} = 214.84$ $u_{22} = 609.18$
 $u_{31} = 176.06$ $u_{32} = 532.54$ $u_{33} = 637.19$
 $u_{41} = 146.71$ $u_{42} = 514.08$ $u_{43} = 590.60$ $u_{44} = 714.34$

Control:

$u_{11} = 429.65$
 $u_{21} = 245.51$ $u_{22} = 590.56$
 $u_{31} = 210.38$ $u_{32} = 520.42$ $u_{33} = 603.15$
 $u_{41} = 254.93$ $u_{42} = 533.15$ $u_{43} = 535.36$ $u_{44} = 643.20$

Table 3: Sample Size Estimations

Endpoints	N per Arm	Power (%)	Total N*
Monocular Visual Acuity 20/40 or better	90	> 90	207
Corneal Staining < Grade 3	116	> 85	270
Acceptable Lens Fit	90	> 90	207
Absolute Rotation within 10-degree	90	> 90	207
Stability with Blink within 5-degree	90	> 90	207
CLUE Comfort	90	> 90	207

*Total N includes ~15% dropout rate

Optimal sample size and its corresponding power for each study endpoint are presented in Table 3. It is determined that a total of 270 subjects (135 per arm) will be sufficient to demonstrate statistical acceptance of both primary and secondary hypotheses.

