6.2.1. Definition

Monocular Visual Acuity (VA) 20/20 or better

Monocular visual acuity (VA) with the study lenses will be assessed using a Snellen distance VA chart at an optical distance of 20 feet throughout the study. Observed monocular VA collected at fitting (Visit 1) will be dichotomized whether VA was '20/20 or better' (refer as 'suitable VA') or 'worse'. VA of 20/20 with a negative modifier will consider to be worse than 20/20. Each eye/subject will be categorized into two groups such that 'response=1' if an eye had suitable VA at fitting or 'response=0' otherwise.

CLUE Score

Subjective CLUE comfort and handling score will be assessed using the Contact Lens User Experience™ (CLUE) questionnaire (Wirth and Houts, 2016⁴). CLUE is a validated patient-reported outcomes (PRO) questionnaire to assess patient-experience attributes of soft contact lenses (comfort, vision, handling, and packaging) in a contact-lens wearing population in the US, ages 18-65. Derived CLUE scores using Item

Response Theory (IRT) follow a normal distribution with a population average score of 60 (SD 20), where higher scores indicate a more favorable/positive response. A 5-point increase in an average CLUE score translates into 10% shift in the distribution of scores for population of soft disposable contact lens wearers.

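### The plan calls 270 subjects sufficient for the secondary hypotheses, but VA 20/20 and CLUE handling were not sized, and VA 20/20 has only about 30–64% power at the SAP's odds-ratio margin of 0.5 under the SAP's own rates

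*SAP*

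**What the plan says.** SAP 1.5 opens by saying that the sample size was "calculated to attain the optimal number of subjects to demonstrate the statistical acceptance of the primary and secondary hypotheses". Below Table 3 it says "Optimal sample size and its corresponding power for each study endpoint are presented in Table 3", and then that "a total of 270 subjects (135 per arm) will be sufficient to demonstrate statistical acceptance of both primary and secondary hypotheses". Protocol 9.2 carries the same sufficiency sentence.

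Table 3 and the matching Protocol 9.2 table have six rows: the five primary endpoints and CLUE comfort. VA 20/20, the first secondary hypothesis, appears only in the SAP's table of historical rates ("Monocular Visual Acuity 20/20 or better", 93.2% test and 92.9% control, labelled Overall). CLUE handling has no sample-size row either.

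The VA 20/20 criterion is stated in four places:

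- Protocol 4.1: a margin of 10% on the proportion.
- Protocol 9.1: an odds-ratio margin of 0.4, tied to 10 points at a 93% reference rate.
- SAP 1.4.2: a "non-inferiority margin (0.5) that reflects 10% difference in distribution between the Atlas A and AOA groups using the reference rate of 89"%.
- SAP 6.2.2: the decision sentence uses 0.5; the next sentence equates 0.4 with 10 points at 89%.

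SAP 1.1 gives the SAP precedence over Protocol Section 9. Protocol 4.1 lies outside that section.

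**The concern.** A sentence that declares the sample sufficient for the secondary hypotheses, next to one that says every endpoint's power is tabulated, tells the reader that VA 20/20 was sized. It was not, and its decision threshold is not settled.

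If the lenses perform as in the historical data, non-inferiority on VA 20/20 would be shown about half the time or less under the SAP's rule. A miss could then be read as a finding about the lens when it reflects the margin and the sample size.

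**Working it through.** **The plan's own figure.** The largest row is corneal staining, 116 per arm. Adding about 15%: 2 × 116 × 1.15 = 267, or 2 × 116 / 0.85 = 273, consistent with the printed 270. The rows at 90 per arm give 2 × 90 × 1.15 = 207, as printed. Completers: 135 × 0.85 = 114.75, the targeted 115 per arm. So 270 comes from the staining row. There is no printed VA 20/20 power to reproduce.

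**Inputs for VA 20/20**

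- Rule: lower two-sided 95% limit of the odds ratio above 0.5 (SAP 1.4.2; decision sentence of SAP 6.2.2).
- n = 115 per arm, two eyes each (SAP 1.3; the per-protocol set of SAP 2.3.1).
- Rates: 89% in both arms (SAP reference rate), or 93.2% against 92.9% (SAP Table 2). The latter are Overall rates, whereas under SAP 6.2.1 "Observed monocular VA collected at fitting (Visit 1) will be dichotomized whether VA was" the criterion was met. No fitting-visit rate is printed.
- Between-eye correlation ρ: none is printed for this endpoint. For the 80%-threshold endpoints the SAP writes "Assuming a correlation of 0.8 between eyes"; for staining, "a correlation between eyes within a subject was set to 0.3". Both are borrowed here as assumptions, and the full range 0 to 1 is shown.

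**Formula** (Wald, population-averaged odds ratio)

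SE² = (1 + ρ)/(2n) × [1/(pT(1 − pT)) + 1/(pC(1 − pC))]

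Power = Φ((ln OR_true − ln margin)/SE − 1.96)

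*89% in both arms, ρ = 0:* SE = √(20.43/230) = 0.298; 0.693/0.298 − 1.96 = 0.37; power 64%.

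*93.2% against 92.9%, ρ = 0:* ln OR_true = 0.046; SE = √(30.94/230) = 0.367; (0.046 + 0.693)/0.367 − 1.96 = 0.06; power 52%.

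| Power, 115 per arm | ρ = 0 | 0.3 | 0.8 | 1 |
|---|---|---|---|---|
| Margin 0.5, 89/89% | 64% | 53% | 41% | 38% |
| Margin 0.5, 93.2/92.9% | 52% | 42% | 32% | 30% |
| Margin 0.4, 89/89% | 87% | 77% | 63% | 59% |
| Margin 0.4, 93.2/92.9% | 75% | 63% | 50% | 46% |

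Simulation of clustered binary data (40,000 trials) at margin 0.5 and ρ = 0, 0.3, 0.8 gives 64.0, 52.8 and 40.7% at 89%, and 51.7, 42.2 and 31.6% at the historical rates.

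With all 135 per arm at margin 0.5, the best case (89%, ρ = 0) is 71%.

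At margin 0.4, 89% and 115 per arm, 80% power requires 1 + ρ ≤ 115 × 0.0979 × (0.916/2.802)² = 1.204, so ρ below about 0.20.

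**What the margins mean in points**

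| Reference rate | OR 0.5 | OR 0.4 | OR equal to a 10-point loss |
|---|---|---|---|
| 89% | 8.8 points | 12.6 points | (0.79/0.21)/(0.89/0.11) = 0.465 |
| 93% | 6.1 points | 8.8 points | (0.83/0.17)/(0.93/0.07) = 0.367 |

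No printed pair of margin and rate equals 10 points exactly.

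**The 10-point hypothesis of Protocol 4.1, tested as a difference.** SE² = (1 + ρ)/(2n) × [pT(1 − pT) + pC(1 − pC)]. At 115 per arm and ρ = 0.8 to 0.3, power is 90–97% at the historical rates (SE 0.0318 to 0.0270) and 72–85% at 89% (SE 0.0391 to 0.0333). This is not the planned analysis.

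**The case against.** The strongest reply is that the shortfall is mainly one of margin. On the 10-point scale of Protocol 4.1 the same sample does well at the historical rates. This stands: much of the loss comes from the odds-ratio conversion, so the margin should be settled before any power figure is quoted.

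Three further points also stand.

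- No power target is printed for VA 20/20. The 80% yardstick is borrowed from the staining row, the lower of the plan's two stated minimums (80% and 90%).
- SAP 6.2.2 specifies a model with random effects for subject and for eye within subject. The figures above are for a population-averaged odds ratio; power under the planned model was not computed.
- The completer target is a minimum, and the endpoint is a secondary one, tested only if every primary hypothesis is met.

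A reader might infer that 64% is an absolute ceiling. The documents do not support that. It holds for the printed rates, 115 per arm and non-negative eye correlation. With equal rates and independent eyes, power at margin 0.5 would be 71% at a true rate of 87%, 76% at 85% and about 80% at 83%; a truly better test lens would also raise it.

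A reader might also infer that no printed combination reaches 80%. That is not so: SAP 6.2.2 itself pairs 0.4 with 89%, which reaches 80% at an eye correlation below about 0.20.

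None of this supplies the missing rows or makes the sufficiency sentence true for VA 20/20.

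**Conclusion.** The concern holds in this form. The statements that all endpoints have tabulated power and that 270 subjects suffice for the secondary hypotheses are wrong as written, because VA 20/20 and CLUE handling have no row. That part needs no assumption.

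For VA 20/20 at the SAP's operative margin of 0.5 and 115 per arm, power is 38–64% at 89% and 30–52% at the historical rates. At 0.4 it is 59–87% and 46–75%. These figures rest on the printed rates (the historical ones being Overall, not fitting-visit), non-negative eye correlation, a two-sided 95% interval and a population-averaged Wald test.

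The margin contradiction is real and sits in consecutive sentences of SAP 6.2.2.

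A reader might go on to conclude that the trial is too small or that its success criterion is at risk. The documents do not support that: study success rests on the primary hypotheses, and this calculation concerns one secondary claim.

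**What to change.** 1. Settle one margin and one reference rate for VA 20/20 across SAP 1.4.2, both sentences of SAP 6.2.2 and Protocol 9.1, and reconcile them with the 10% in Protocol 4.1.
2. In SAP 1.5, correct the statement that Table 3 covers every endpoint. In SAP 1.5 and Protocol 9.2, limit the sufficiency sentence to the endpoints actually sized. As the tables stand, that excludes VA 20/20 and CLUE handling.
3. Either add a VA 20/20 row with the sponsor's own power for the planned model at the reconciled margin, stating the fitting-visit rates and eye correlation assumed, or state that VA 20/20 is not powered. The ranges given here show the size of the problem and should not be copied in as table entries.

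Cost: the margin wording, a few sentences and at most one table row in each document, plus one power calculation if the row is added. No change to enrolment or conduct. It is best done before unmasking.
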